#### 3.2. Null and alternative hypothesis

Per ICH E14 [2], a “negative” (successful) ‘thorough QT/QTc trial’ is one in which the upper bound of the 95% one-sided confidence interval for the largest time-matched placebo-corrected, change-from-baseline mean effect of the drug on the QTc interval excludes 10 ms.

Consequently, the trial must show that both 0.1 and 0.3 mmol/kg doses of P03277 do not increase the QT interval corrected by Fridericia formula (QTcF) at all timepoints.

##### Primary Analysis

The null hypothesis is that the difference between each of the two doses of P03277 and placebo for the largest mean change from baseline for the QTcF is greater or equal than the non-inferiority margin set to 10 ms according to regulatory guidance.

CONFIDENTIAL	
STATISTICAL ANALYSIS PLAN N° GDX-44-006
 
VERSION N° 2.0      DATED: 24JUL2018
 
██████████
	
██████████
 
Page 13 / 57

--------------	--	---

An Intersection-Union test is performed at a one-sided 5% significance level. This is equivalent to compare at each timepoint the upper limit of the two-sided 90% confidence intervals of the difference between each of the two doses of P03277 and placebo with the non-inferiority margin of 10 ms:

- $\mu_{ij}$  is the expected average of QTcF for each dose of P03277 at each timepoint (where  $i$  is corresponding to one timepoint and  $j$  to the 2 doses)
- $\mu_{ij0}$  is the expected average of QTcF for corresponding placebo

Null hypothesis:

$$H_0: \mu_{ij} - \mu_{ij0} \geq 10, i = 1 \dots 11, j = 1, 2$$

Alternative hypothesis:

$$K_0: \mu_{ij} - \mu_{ij0} < 10, i = 1 \dots 11, j = 1, 2.$$

To conclude that P03277 is non-inferior to placebo, the null hypothesis has to be rejected for all timepoints and both doses simultaneously hence the overall Type I error rate does not need to be adjusted.

#### Assay sensitivity

Assay sensitivity assessment is defined as the largest time-matched placebo-corrected, change-from-baseline mean effect of moxifloxacin of QT interval expressed as QTc according to Fridericia's formula (in ms).

In order to validate the assay sensitivity of the trial, the positive control must increase the QTcF by at least 5 ms for at least one timepoint.

The null hypothesis is that the difference between the positive control and placebo for the mean change from baseline for the QTcF is less than 5 ms according to regulatory guidance.

This test is performed one-sided at the 5% significance level which is equivalent to compare the lower limit of the two-sided 90% confidence intervals of the difference with 5 ms:

- $\mu_i$  is the expected average of QTcF for positive control at each timepoint (where  $i$  is corresponding to one timepoint)
- $\mu_{i0}$  is the expected average of QTcF for corresponding placebo

Null hypothesis

$$H_0: \mu_i - \mu_{i0} < 5, i = 1 \dots 5$$

Alternative hypothesis

$$K_0: \mu_i - \mu_{i0} \geq 5, i = 1 \dots 5$$

To conclude that positive control is superior to placebo, the null hypothesis has to be rejected for at least one timepoint.

As multiple timepoints are examined separately, the overall Type I error rate needs to be adjusted.

To address this issue, the method described by Hochberg and Tamhane [3] will be used.

To minimize the correction and because the positive control effect is well known, only five timepoints around the peak effect will be used: 1h, 1h30, 2h, 3h and 4h.

CONFIDENTIAL	STATISTICAL ANALYSIS PLAN N° GDX-44-006  VERSION N° 2.0      DATED: 24JUL2018  [REDACTED]	[REDACTED]  Page 14 / 57
--------------	---	--------------------------------

### 3.3. Determination of sample size

A total of 48 subjects will be included in the study trial.

The sample size is determined using published recommendations for a thorough QT trial [4].

$N$  can be estimated by 
$$N = 2 * [t_{\alpha}(\gamma) + t_{\beta'}(\gamma)]^2 [\sigma / (\delta - 10)]^2$$

where

- $\sigma^2$  is the within subject variability
- $\gamma = N - 2$
- $\beta' = 1 - (1 - \beta)1/L$  where  $\beta$  is the Type II error and  $L$  the number of measurements
- $\alpha$  is the Type I error
- $t_{\alpha}(\gamma)$  the critical values for a Student T distribution with  $\gamma$  degrees of freedom at an  $\alpha$  level.
- $\delta$  is the expected difference between active drug and placebo (0 if no difference expected, >0 if drug is expected to slightly increase QT).

Considering an expected intra-variability of the primary endpoint of  $\sigma = 9$  ms and an expected difference of  $\delta = 2$  ms between P03277 (two doses) and placebo, 40 subjects are needed to demonstrate non-inferiority with a non-inferiority margin of 10 ms, a power of  $1 - \beta = 85\%$  and a Type I error of  $\alpha = 5\%$  one-sided on the  $L = 9$  measurements.

This sample size is also sufficient to detect a difference of 5 ms (with an expected difference of 12 ms for at least one timepoint and an expected intra-variability of the primary endpoint of  $\sigma = 9$  ms) of the primary endpoint between moxifloxacin and placebo with a power of 85%.

To account for potential dropouts and/or unevaluable data points, 48 subjects will be randomized in the trial. The recruitment could be stopped before 48 subjects from the time the number of fully evaluable subjects for the primary criterion is 40. That is to say having took part to the study, until the last scheduled ECG holter recording.

A dropout is a subject who is prematurely discontinuing the trial before the end of the last holter ECG recording.

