11.2 Sample Size

A total of 48 subjects will be included in the study trial.

The sample size is determined using published recommendations for a thorough QT trial (Statistical Issues Including Design and Sample Size Calculation in Thorough QT/QTc Studies [4]).

N can be estimated by $N = 2 * (t_{\alpha}(\gamma) + t_{\beta}(\gamma))^2 [\sigma / (\delta - 10)]^2$

where

- σ^2 is the within subject variability
- $\gamma = N - 2$
- $\beta' = 1 - (1 - \beta)^{1/L}$ where β is the Type II error and L the number of measurements
- α is the Type I error
- $t_{\alpha}(\gamma)$ the critical values for a Student T distribution with γ degrees of freedom at an α level.
- δ is the expected difference between active drug and placebo (0 if no difference expected, >0 if drug is expected to slightly increase QT)

Considering an expected intra-variability of the primary endpoint of $\sigma = 9$ ms and an expected difference of $\delta = 2$ ms between P03277 (two doses) and placebo, 40 subjects are needed to demonstrate non-inferiority with a non-inferiority margin of 10 ms, a power of $1 - \beta = 85\%$ and a Type I error of $\alpha = 5\%$ one-sided on the $L = 9$ measurements.

This sample size is also sufficient to detect a difference of 5 ms (with an expected difference of 12 ms for at least one timepoint and an expected intra-variability of the primary endpoint of $\sigma = 9$ ms) of the primary endpoint between moxifloxacin and placebo with a power of 85%.

To account for potential dropouts and/or unevaluable data points, 48 subjects will be randomized in the trial. The recruitment could be stopped before 48 subjects from the time the number of fully evaluable subjects for the primary criterion is 40. That is to say having took part to the study, till the last scheduled ECG Holter recording.

A dropout is a subject who is prematurely discontinuing the trial before the end of the last Holter ECG recording.

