### 1.2. Study design

GDX-44-006 is a Phase I, single center, randomized, cross-over double-blind placebo-controlled and open-label positive-controlled trial which aims to assess the electrocardiographic safety of a new gadolinium-based contrast agent P03277 in healthy volunteers.

Subjects included in the trial should be administered with three Investigational Medicinal Products (IMPs) and one Auxiliary Medicinal Product (AMP) in a 4\*4 cross over sequence according to a William design balanced for first order carry over effect. Twelve subjects will be assigned to each sequence (6 males and 6 females). The volunteers will be enrolled sequentially by cohort of 8 subjects. Sequence and IMP/AMP will be randomly assigned to subjects.

The three IMPs will be:

- P = Placebo (Nacl 0.9%)
- CD = P03277 tested at anticipated clinical dose (0.1mmol/kg)
- SD = P03277 tested at supra-clinical dose (0.3mmol/kg).

The AMP will be:

- PC = Positive control (moxifloxacin 400 mg - per os).

Period's duration for moxifloxacin, placebo, P03277 at clinical dose and P03277 at supra-clinical dose will each be 72 hours. The total duration for all periods (confinement) will be 12 days.

After all eligibility requirements satisfied, subject will be randomized to a sequence of IMP/AMP administration. Each subject will be monitored with a 12-lead Holter electrocardiogram (ECG) from 1 hour before any product administration until 24 hours post-administration.

ECGs parameters will be measured as triplicate based on the following timepoints from the 12-lead Holter ECG monitoring:

CONFIDENTIAL	STATISTICAL ANALYSIS PLAN N° GDX-44-006  VERSION N° 2.0      DATED: 24JUL2018  [REDACTED]	[REDACTED]  Page 7 / 57
--------------	---	-------------------------------

- moxifloxacin: pre-dose up to 24 hours post-dose: [-1 hour, 30 min, 1 hour, 1.5 hours, 2 hours, 3 hours, 4 hours, 8 hours, 24 hours]
- P03277 and Placebo: pre-dose up to 24 hours post-dose: [-1 hour, 5 min, 10 min, 20 min, 30 min, 1 hour, 1.5 hours, 2 hours, 3 hours, 4 hours, 8 hours, 24 hours].

ECG measurements will be compared with ECG parameters collected after administration of placebo (Nacl 0.9%). The test sensitivity will be assessed using a positive control (moxifloxacin 400 mg per os) known to induce delays in QT intervals.

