### **3.8. Multiple comparisons/multiplicity**

The multiplicity is handled by considering a study “negative” (i.e. successful) if both P03277 doses reject simultaneously the null hypothesis for all timepoints and if for the assay sensitivity, the null hypothesis is rejected for at least one timepoint, using the method described by Hochberg and Tamhane to deal with multiple timepoints.

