## **4. CHANGES IN THE CONDUCT OF THE STUDY OR PLANNED ANALYSES**

Primary analysis will test each timepoint: 11 instead of 9 mentioned in the protocol.

A model will be performed for each timepoint, the time will no more be included in the model. There is no change on the statistical analysis as Intersection-Union test was planned.

In secondary analysis, same analysis as for primary endpoint will be repeated for HR in addition of QT, QTcPOP and QTcB.

Descriptive analysis on number and percentage of subjects showing values above predefined threshold will be presented for PR and QRS.

CONFIDENTIAL	
STATISTICAL ANALYSIS PLAN N° GDX-44-006
 
VERSION N° 2.0      DATED: 24JUL2018
 
██████████
	
██████████
 
Page 16 / 57

--------------	--	---

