#### Test

Differences between means will be tested through the model for each timepoint and for the two doses of P03277 using Student's t-test.

For each timepoint, the two-sided 90% confidence intervals of the difference between each of the two doses of P03277 and placebo is calculated for testing the hypotheses.

The trial will be considered as successful if no test is significant that is to say if the upper range of the 90% CI is lower than 10 ms for all tests.

The appropriateness of a linear model will be assured by inspecting the goodness of fit by looking at normal QQ plots for the residuals and plots of the residuals over predicted values.

The primary analysis will be performed using the Per Protocol Set.

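### The stated 85% power at 40 evaluable subjects covers one dose only; for the both-doses success rule the plan's own formula gives about 74%

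*SAP*

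**What the plan says.** Protocol 11.2 and SAP 3.3 use one formula, `N = 2 × [t_α(N−2) + t_β′(N−2)]² × [σ/(δ−10)]²`, with `β′ = 1 − (1−β)^(1/L)`. The inputs are σ = 9 ms, δ = 2 ms for the two doses, one-sided α = 5%, power 85% and L = 9. The conclusion is that "40 subjects are needed to demonstrate non-inferiority with a non-inferiority margin of 10 ms".

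The success rule is wider than L = 9. SAP 3.2 says: "To conclude that P03277 is non-inferior to placebo, the null hypothesis has to be rejected for all timepoints and both doses simultaneously". SAP 3.8 repeats it: the study is negative "if both P03277 doses reject simultaneously the null hypothesis for all timepoints", with assay sensitivity as a further condition. Protocol 11.3.6 indexes timepoints by i = 1 to 9 and doses separately by j = 1, 2. SAP section 4 then announces: "Primary analysis will test each timepoint: 11 instead of 9 mentioned in the protocol". SAP 3.3 still has L = 9.

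On numbers, "To account for potential dropouts and/or unevaluable data points, 48 subjects will be randomized in the trial", but protocol 11.2 adds: "The recruitment could be stopped before 48 subjects from the time the number of fully evaluable subjects for the primary criterion is 40". SAP 1.2 notes that "The volunteers will be enrolled sequentially by cohort of 8 subjects". On the analysis population, SAP 5.5.1.2 says: "The primary analysis will be performed using the Per Protocol Set".

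**The concern.** In this formula L is the number of tests that must all succeed: β′ is the Type II error allowed to each test so that L independent tests pass together with probability 1 − β. The plan makes that allowance across timepoints but not across doses. The 85% therefore describes one dose passing, while the trial needs two.

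What is at stake is the risk of a false failure, meaning that a drug with only a 2 ms effect misses the criterion at one of the 22 comparisons. The same 85% justifies 40 as an adequate number, so anyone deciding whether to stop recruitment at 40 would rely on a figure that does not describe the trial's own criterion.

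**Working it through.** **Inputs** (protocol 11.2, SAP 3.3): σ = 9 ms, δ = 2 ms, margin 10 ms, one-sided α = 0.05, β = 0.15. Comparisons: 9 timepoints (protocol) or 11 (SAP 3.2 and 4), times 2 doses.

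**Reproducing the stated figure.** The formula is solved iteratively, with [σ/(δ−10)]² = (9/8)².

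| L | What it counts | β′ | N from formula | Rounded up |
|---|---|---|---|---|
| 9 | one dose, protocol timepoints | 0.0179 | 37.90 | 38 |
| 11 | one dose, SAP timepoints | 0.0147 | 39.54 | 40 |
| 18 | both doses, protocol timepoints | 0.0090 | 43.51 | 44 |
| 22 | both doses, SAP timepoints | 0.0074 | 45.13 | 46 |

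The stated 40 is close to the result for L = 9 and equals the result for one dose at 11 timepoints. The move from 9 to 11 timepoints is disclosed and does no harm by itself.

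**Power at 40, by inverting the same formula.**
- Standard error of a difference: 9 × √(2/40) = 2.012 ms.
- (10 − 2)/2.012 = 3.975, and t at 0.05 with 38 df is 1.686, so t_β′ = 3.975 − 1.686 = 2.289.
- Power of one comparison: P(T with 38 df < 2.289) = 0.98615.
- Joint power: 0.98615^9 = 88.2%; ^11 = 85.8%; ^18 = 77.8%; ^22 = 73.6%.

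An exact noncentral t calculation gives 76.7% for L = 22, still below 85%.

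**Other evaluable numbers**, formula with L = 22: 38, 67.5%; 39, 70.7%; 44, 82.9%; 46, 86.4%; 47, 87.9%; 48, 89.3%.

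**Relaxing independence.** The formula treats all 22 comparisons as independent, although both doses are compared with the same placebo period. The figures below are simulated joint power at N = 40 with a shared placebo, σ = 9 ms and 11 timepoints × 2 doses. Ranges span 38 (N − 2) to 113 (3N − 7) residual degrees of freedom. The correlations and non-flat profiles are my assumptions; the documents give none.

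| Assumption | Joint power at 40 |
|---|---|
| 2 ms throughout, timepoints uncorrelated | 78-80% |
| 2 ms throughout, equal correlation 0.4 | 84-86% |
| 2 ms throughout, equal correlation 0.5 | 85-87% |
| 2 ms throughout, serial correlation 0.65 | 83-85% |
| 2 ms throughout, serial correlation 0.75 | 86-87% |
| Uncorrelated, 2 ms at four timepoints and 1 ms at seven, both doses | 88-89% |
| Uncorrelated, 1 ms at lower dose and 2 ms at higher | 85-87% |

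Within this model zero correlation is a lower boundary, because several timepoints are minutes apart and share one baseline. By the formula with L = 22, 85% at 40 would need a flat effect of about 1.46 ms instead of 2 ms. At 47 evaluable, the first row of the table becomes 91-92%.

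**The case against.** The best defence is that true power at 40 may well be 85% or more, and that the shortfall is confined to a narrow range.

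- **Correlation.** At an equal correlation of about 0.5 there is no shortfall at 40. This stands as a possibility, but the plan's formula assumes independence and no correlation is stated.
- **Residual SD.** The primary model adjusts for baseline QTcF, so the residual SD could be below 9 ms. With uncorrelated timepoints and a shared placebo, 8.75 ms gives 83-85% and 8.6 ms gives 86-87%. But 9 ms is the plan's stated input, and a smaller value would be a new assumption.
- **Effect profile.** The endpoint is the largest effect, so 2 ms might be read as a maximum, with smaller effects elsewhere. The wording leaves room for that, but the formula applies δ to every measurement.
- **The 74% is pessimistic.** It lies below the 78-80% obtained once the placebo period is shared. That is correct, so it should be quoted only as the result of the plan's formula.
- **The arithmetic reproduces.** It does for one dose; the fault is in what L counts, not in the calculation.
- **Narrow window.** With 48 randomized, flat 2 ms, no correlation and a shared placebo, 43 evaluable already gives 85-86%. Stopping at 40 is optional, and with cohorts of 8 it saves a cohort only if the first five have no loss (5 × 8 = 40). This limits the practical effect but does not remove it. Protocol 11.2 defines fully evaluable as taking part up to the last scheduled Holter recording, whereas the Per Protocol Set also drops subjects with any major deviation. An early stop could therefore leave fewer than 40 in the primary analysis.

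**Conclusion.** The concern holds. The plan's 85% at 40 evaluable is a one-dose figure. For the rule that decides the trial, the plan's own method gives 73.6% (77.8% if only the protocol's nine timepoints are counted), so the risk of false failure is about 26% against the 15% implied. With a shared placebo and uncorrelated timepoints that risk is 20-22%. These figures rest on σ = 9 ms and a 2 ms effect at every timepoint for both doses. Almost all of the gap comes from the second dose.

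This is an unsupported power statement, not evidence that the trial is underpowered. Estimates, confidence intervals, Type I error and the decision rule are untouched. The consequence is real mainly if recruitment stops at 40 evaluable, or if about 8 of 48 are lost. A correction should be made, but it is one of text.

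**What to change.** In protocol 11.2 and SAP 3.3, replace L = 9 with the 11 timepoints × 2 doses that are tested, and restate the power at 40 evaluable for both doses passing. Give one of the following:

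- about 74%, labelled as the plan's formula with all comparisons treated as independent; or
- a single value under one stated and justified assumption about between-timepoint correlation and effect profile, for example 78-80% with shared placebo and no between-timepoint correlation, or 85-87% at an equal correlation of 0.5.

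If 89% is quoted, say that it comes from the formula and applies to 48 evaluable, not 48 randomized. Keep the option to stop at 40, with the restated figure beside it.

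The cost is text and figures in two sections. No extra subjects are needed, and the analysis, decision rule and stopping option do not change. The drawback is a stated power that is lower or openly conditional.

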### 3.4. Adjustment for covariates

For the primary analysis and the assay sensitivity, QTcF at baseline and sex are considered as covariates taken into account in the models used for the analyses.

### 3.5. Handling of dropouts or missing data

No imputation will be performed in this trial.

### 3.6. Interim analyses and data monitoring

Safety analysis will be performed for data monitoring committee (DMC) during the trial.

CONFIDENTIAL	
STATISTICAL ANALYSIS PLAN N° GDX-44-006
 
VERSION N° 2.0      DATED: 24JUL2018
	
[REDACTED]
 
Page 15 / 57

--------------	--	---

### **3.7. Multicenter studies**

Not Applicable.

### **3.8. Multiple comparisons/multiplicity**

The multiplicity is handled by considering a study “negative” (i.e. successful) if both P03277 doses reject simultaneously the null hypothesis for all timepoints and if for the assay sensitivity, the null hypothesis is rejected for at least one timepoint, using the method described by Hochberg and Tamhane to deal with multiple timepoints.

### **3.9. Use of a subset of subjects for cardiac safety analysis**

The primary analysis will be done using the Per Protocol Set and will be repeated using the Full Analysis Set.

The assay sensitivity analysis will be done using the Full Analysis Set and repeated using the Per Protocol Set.

### **3.10. Active control studies intended to show equivalence**

Not Applicable.

### **3.11. Examinations of subgroups**

The trial is stratified by sex which will be taken into account for the primary analysis and the assay sensitivity by putting it in the model. No other examination of subgroups is planned.

## **4. CHANGES IN THE CONDUCT OF THE STUDY OR PLANNED ANALYSES**

Primary analysis will test each timepoint: 11 instead of 9 mentioned in the protocol.

A model will be performed for each timepoint, the time will no more be included in the model. There is no change on the statistical analysis as Intersection-Union test was planned.

In secondary analysis, same analysis as for primary endpoint will be repeated for HR in addition of QT, QTcPOP and QTcB.

Descriptive analysis on number and percentage of subjects showing values above predefined threshold will be presented for PR and QRS.

CONFIDENTIAL	
STATISTICAL ANALYSIS PLAN N° GDX-44-006
 
VERSION N° 2.0      DATED: 24JUL2018
 
██████████
	
██████████
 
Page 16 / 57

--------------	--	---

## 5. STATISTICAL AND ANALYTICAL PLANS

### 5.1. Disposition of subjects

Subject disposition will be based on all subjects who have signed their informed consent form and tabulated by sequence and overall for the following categories:

- Total number of subjects included;
- Total number of subjects exposed to each trial product;
- Number (percentage) of subjects completing the study;
- Number (percentage) of subjects prematurely discontinuing from study.

Reason of screen-failure and premature discontinuation will be presented.

### 5.2. Data sets analysed and protocol deviations

#### Data sets analysed

There will be four subject sets defined for this study: All enrolled subjects set, the Safety Set (SS), the Full Analysis Set (FAS) and the Per-Protocol Set (PPS).

All enrolled Subjects Set will include all subjects who signed their informed consent form. This set will be used for subject disposition summaries and individual listings.

All subjects who failed the screening visit (not selected) or withdrawn from the study before the randomization are screen-failed subjects and will be presented in the all enrolled data set. Those subjects have different data collected depending on the selection status i.e. complete screening visit and inclusion visit data collected for volunteers who have been selected at screening visit while only screening visit data were collected for subjects who did not comply with the eligibility criteria.

The Safety Set will include all subjects receiving at least one administration of IMP, regardless of the quantity. This set will be used for evaluation of safety and description of demographic data and baseline characteristics.

The Full Analysis Set will include all randomized subjects. This set will be used for evaluation of cardiac safety and description of demographic data and baseline characteristics.

The Per Protocol Set will be a subset of the FAS and will include all subjects who have no major protocol deviations throughout their whole trial period. Major deviations will be defined as having an impact on the primary criterion. Primary analysis will be performed on this set.

The number of subjects by analysis set will be tabulated by sequence group and overall.

The following table describes how the above defined subjects sets will be used in the different analyses conducted.

CONFIDENTIAL	STATISTICAL ANALYSIS PLAN N° GDX-44-006  VERSION N° 2.0      DATED: 24JUL2018  	  Page 17 / 57
--------------	--	---

Analyses Sets	Safety Set	Full Analysis Set (FAS)	Per protocol (PP) Set
Demographic data and baseline characteristics	✓	✓	✓ *
Exposure	✓		
Cardiac safety assessment		✓	✓
Safety assessment	✓		

\*: If the difference between FAS and PP set is greater than 10%

